5.3.2 Other Safety Analysis

5.3.2.1 Adverse Events

The applicable definition of an AE is in the study protocol. All AEs occurring from when a subject signs informed consent to when a subject exits the study will be accounted for in the reporting. Analysis and presentation of pre-treatment AEs will be separated from treatment-emergent AEs occurring during the study period. A pre-treatment AE is an event that occurs after signing informed consent but prior to exposure to the study lens [REDACTED]

[REDACTED] The period for treatment-emergent AE analysis starts from exposure to study lens until the subject completes or is discontinued from the study.

Descriptive summaries (counts and percentages) for ocular and nonocular AEs will be presented by Medical Dictionary for Regulatory Activities (MedDRA) Preferred Terms (PT). Additionally, relationship to lens will be identified in all AE tables. Unit of presentation for ocular AEs will be eye and nonocular AEs will be subject.

Individual subject listings will be provided for both pre-treatment and treatment-emergent AEs, where any AE leading to study discontinuation will be indicated.

[figure not shown]
[figure not shown]
5.3.3 Biomicroscopy Findings/Slit Lamp Examination

Biomicroscopy assessment will be performed at all study visits, including Visit 1 to 9 and unscheduled visits. The reporting unit for each biomicroscopy finding will be eye.

A summary of grade category counts and percentages will be presented for each parameter at each scheduled visit and all unscheduled visits combined. A listing of "Other" slit lamp findings will also be provided.

5.3.4 Device Deficiencies

A frequency table showing counts for each treatment-emergent Device Deficiency category will be presented. In addition, listings for treatment-emergent and pre-treatment device deficiencies will be provided.

[figure not shown]

[figure not shown]
7

Sample Size and Power Calculations

Sample size calculation was based on extended wear clinical studies from three previous PMA submissions [REDACTED] and one 52-week extended wear study [REDACTED] that evaluated 5 currently marketed silicone hydrogel contact lenses. The weighted average, based on sample size, on the proportion of ocular serious or significant non-serious ADEs obtained from these five contact lenses was 0.045. Therefore, assuming that the expected difference between test and control is 0 and that the control proportion is 0.045, a sample size of 213 per group will provide 80% power to reject the null hypothesis of inferiority in test compared to control, with a noninferiority margin of 0.05 (5%).

Taking into consideration the exposure duration of 12 months, approximately 568 subjects will be randomized (284 test and 284 control) to compensate for approximately 25% drop-out rate.

[figure not shown]

[figure not shown]
[figure not shown]
[figure not shown]

10 Revision History

[figure not shown]
[figure not shown]
Revision 4

[figure not shown]
This is the fourth revision (Version 5.0) of the Statistical Analysis Plan for this study. This version of the Statistical Analysis Plan is based on Version 5.0 of the study protocol.

[figure not shown]
[figure not shown]

[figure not shown]

11 Appendix

Table 11-1 Schedule of Study Procedures and Assessments^a

Procedure/Assessment	Baseline	Follow-Up Visits								Exit	Early Exit	USV
	Visit 1	Visit 2	Visit 3	Visit 4	Visit 5	Visit 6	Visit 7	Visit 8	Visit 9			
	Day 1 Dispense	24 hrs	1-week	1-month	2-months	3-months	6-months	9-months	12-months			
Informed Consent	✓	-	-	-	-	-	-	-	-	-	-	-
Demographics	✓	-	-	-	-	-	-	-	-	-	-	-
Medical History including pregnancy ¹	✓	✓	✓	✓	✓	✓	✓	✓	✓	✓	✓	(✓)
Concomitant Medications	✓	✓	✓	✓	✓	✓	✓	✓	✓	✓	✓	(✓)
Inclusion/Exclusion	✓	-	-	-	-	-	-	-	-	-	-	-
Habitual lens information (brand / manufacturer, modality, power, wear success, habitual lens care brand)	✓	-	-	-	-	-	-	-	-	-	-	-
Distance VA w/ habitual correction (Snellen)	✓	-	-	-	-	-	-	-	-	✓	✓	(✓)
Manifest refraction	✓	(✓)	(✓)	(✓)	(✓)	(✓)	(✓)	(✓)	(✓)	✓	✓	(✓)
Keratometry	✓	-	-	-	-	-	✓	-	✓	✓	(✓)	
Biomicroscopy ²	✓	✓	✓	✓	✓	✓	✓	✓	✓	✓	✓	✓
Determine study lens fit and power for each eye [REDACTED]	✓	-	-	-	-	-	-	-	-	-	-	-

Procedure/Assessment	Baseline	Follow-Up Visits								Exit	Early Exit	USV
	Visit 1	Visit 2	Visit 3	Visit 4	Visit 5	Visit 6	Visit 7	Visit 8	Visit 9			
	Day 1 Dispense	24 hrs	1-week	1-month	2-months	3-months	6-months	9-months	12-months			
█ O/R as necessary.												
Order study lenses	✓	(✓)	(✓)	(✓)	(✓)	(✓)	(✓)	(✓)	-	-	(✓)	
IP Dispense	✓	(✓)	(✓)	(✓)	(✓)	(✓)	(✓)	(✓)	-	-	(✓)	
Distance VA w/ study lenses (Snellen)	✓	✓	✓	✓	✓	✓	✓	✓	✓	✓	✓	✓

Procedure/Assessment	Baseline	Follow-Up Visits								Exit	Early Exit	USV
	Visit 1	Visit 2	Visit 3	Visit 4	Visit 5	Visit 6	Visit 7	Visit 8	Visit 9			
	Day 1 Dispense	24 hrs	1-week	1-month	2-months	3-months	6-months	9-months	12-months			
Symptoms, problems & complaints ⁴	✓	✓	✓	✓	✓	✓	✓	✓	✓	✓	✓	✓
Study lens and accessories return log	(✓)	✓	✓	✓	✓	✓	✓	✓	✓	✓	✓	(✓)
Adverse events	✓	✓	✓	✓	✓	✓	✓	✓	✓	✓	✓	(✓)
Device deficiencies	✓	✓	✓	✓	✓	✓	✓	✓	✓	✓	✓	(✓)
Exit Form	(✓)	(✓)	(✓)	(✓)	(✓)	(✓)	(✓)	(✓)	(✓)	✓	✓	(✓)

^a See Section 26 of the MOP (Manual of Procedures) for a chronological order of procedures per visit

(✓) assessment performed as necessary, eg, decrease of VA by 2 lines or more with IP.

USV=Unscheduled Visit

¹ Pregnancy to be self-reported by subject

⁴ Symptoms, problems, and complaints will include burning/stinging, itching, lens awareness, dryness, discomfort, blurred vision, fluctuating/variable vision, halo, lens needs cleaning, redness, excessive tearing, secretions, photophobia, and other (description required). The response will be recorded as “present” or “absent”.

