Subject population	
Volunteer subjects aged 18 or over who are adapted daily wear or extended wear frequent replacement soft contact lens wearers, have at least 3 months of soft contact lens wearing experience, and who wear their habitual lenses at least 5 days per week.
 
Subjects must have regularly worn their habitual lenses for at least 10 hours per day. Additionally, extended wear lens wearers must have regularly worn their habitual lenses for at least 1 night per week. Subjects must require contact lens correction in the power range available for this study as specified in the inclusion criteria.
 
[REDACTED]
 
[REDACTED]
 
[REDACTED]
 
[REDACTED] Pregnant and breastfeeding women are excluded from this study.
 
Planned number of subjects for the study: ~812 (total)
 
• Primary Cohort
• [REDACTED]• Enrolled/consented: ~632• Randomized: ~568 (~284 each in test and control)• Completed: at least 426 (minimum 213 completed each in test and control) 
[REDACTED]

	

Key inclusion criteria (See Section 8.1 for a complete list of inclusion criteria)
	
 • Successful wear of spherical daily wear or extended wear frequent replacement soft contact lenses in both eyes during the past 3 months for a minimum of 5 days per week. Habitual daily or extended wear subjects must have regularly worn their lenses for at least 10 hours per day. Additionally, extended wear lens wearers must have regularly worn their lenses for a minimum of 1 night per week. • Manifest cylinder ≤ 0.75 D in each eye. 

Key exclusion criteria (See Section 8.2 for a complete list of exclusion criteria)
	
 • Currently pregnant or breast-feeding • Monovision contact lens wearers

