1.3 Randomization

A member of the Randomization Programming group at Alcon who is not part of the study team will generate the randomized allocation schedule(s) for study lens assignment. Randomization will be implemented in the Electronic Data Capture (EDC)/Interactive Response Technology (IRT) integration system.

Subjects will be randomized in a 1:1 ratio to receive either [REDACTED] or Biofinity contact lenses, respectively. [REDACTED]

[REDACTED]

[REDACTED]

[REDACTED]

Randomization schedule will be blocked to ensure a balance (1:1) in lens allocation within sites.

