5.2 Safety Hypotheses

Primary Safety

The null and alternative hypotheses for the primary analysis are formulated in terms of the predefined margin of 0.05 for noninferiority:

$$H_0: P_T - P_C \geq 0.05$$

$$H_a: P_T - P_C < 0.05$$

where P_T and P_C denote the proportion of eyes reporting ocular serious and significant non-serious ADEs with Mercury and Biofinity contact lenses, respectively.

[figure not shown]
[figure not shown]
Other Safety

No inferences are to be made on other safety endpoints; therefore, no hypotheses are formulated.

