5.3 Statistical Methods for Safety Analyses

5.3.1 Primary Safety Analysis

Proportion of events will be analyzed using a generalized linear model, with a logit link function, accounting for within-subject correlation. Site and Site-by-Treatment interaction terms will also be included to assess potential effect of sites on treatment difference. A one-sided 95% upper confidence limit (UCL) will be calculated for the difference in proportions between treatments (Mercury minus Biofinity), and the null hypothesis will be rejected if $UCL < 0.05$.

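### Is the 80% power figure wrong because it counts subjects while the primary safety test counts eyes?

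*SAP*

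**What the plan says.** SAP section 7, in the same terms as Protocol 12.8, bases the calculation on "assuming that the expected difference between test and control is 0 and that the control proportion is 0.045", with a noninferiority margin of 0.05, and concludes that "a sample size of 213 per group will provide 80% power to reject the null hypothesis of inferiority in test compared to control". The number randomized is then raised to 284 per group for about 25% drop-out.

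The 213 are people. The Protocol Summary (section 3) gives the planned primary cohort as "Completed: at least 426 (minimum 213 completed each in test and control" groups, and SAP Table 1-1 agrees.

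The test is on eyes. In SAP 5.2 the two proportions being compared "denote the proportion of eyes reporting ocular serious and significant non-serious ADEs", and SAP 5.1 defines a present/absent variable for each eye. Protocol 7.1 has each subject wear the assigned lens in both eyes. The model in SAP 5.3.1 has a logit link and allows for within-subject correlation; a one-"sided 95% upper confidence limit (UCL) will be calculated for the difference in proportions" and compared with 0.05. SAP 5.3.1 also puts site and site-by-treatment terms in the model, whereas Protocol 12.6.1.2 does not mention them.

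The visible sample-size text gives no between-eye correlation and no design effect.

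**The concern.** A power statement should describe the test that will be run. Here the calculation treats 213 as a count of independent outcomes, while the test uses two outcomes per subject. If the 213 had been a count of eyes, or if the clustering of eyes had been ignored in the harmful direction, the trial could be short of power on the one comparison that decides study success. Even in the other direction there is a possible cost: the minimum of 213 completers per group might be larger than 80% power requires, and someone judging a shortfall in completers could misread its consequence. The unit also bears on how the historical 0.045 and the 5-point margin are understood.

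**Working it through.** **Inputs.** Rate 0.045 in both groups, difference 0, margin 0.05, 213 per group, 80% power, 25% drop-out (SAP 7, Protocol 12.8). One-sided 5% level (SAP 5.3.1). Equal allocation (SAP 1.3: "Subjects will be randomized in a 1:1 ratio to receive either" lens). Two eyes per subject on the same lens (Protocol 7.1). The between-eye correlation r is not given, so it is taken over 0 to 1 as an assumption.

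**Step 1: the plan's own figure.** With one independent outcome per unit,

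n = (1.645 + 0.8416)² × 2 × 0.045 × 0.955 / 0.05² = 212.6, rounded up to 213.

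Power at n = 213: the standard error is √(2 × 0.045 × 0.955 / 213) = 0.0201, and Φ(0.05/0.0201 − 1.645) = 80.1%. The randomized number is 213/0.75 = 284. All three figures reproduce. A one-sided 2.5% level would have needed 270, so the plan did use 5%.

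**Step 2: the per-eye test.** With n subjects and two eyes each, the variance of a group's proportion of eyes is p(1 − p)(1 + r)/(2n). The effective number of independent outcomes is therefore 2n/(1 + r), which for n = 213 is 426/(1 + r). It equals 213 only when r = 1.

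Power = Φ(0.05/√(2 × 0.045 × 0.955 × (1 + r)/426) − 1.645). As a check, paired-eye data were simulated with a cluster-robust one-sided 95% limit (100,000 runs per setting).

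| r | Effective n per group | Power, formula | Power, simulation | Subjects per group for 80% |
|---|---|---|---|---|
| 0 | 426.0 | 97.0% | 96.9% | 107 |
| 0.25 | 340.8 | 93.4% | 93.0% | 133 |
| 0.5 | 284.0 | 89.1% | 88.9% | 160 |
| 0.75 | 243.4 | 84.5% | 84.3% | 186 |
| 1 | 213.0 | 80.1% | 79.7% | 213 |

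The effective size of 284 at r = 0.5 matches the randomized number only by coincidence (426/1.5 and 213/0.75).

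**Step 3: if 0.045 is a per-subject rate.** If it is the proportion of subjects with an event in either eye, the per-eye rate q solves 2q − [q² + r q(1 − q)] = 0.045. This gives q = 0.0303 at r = 0.5, with power 96.6%, and q = 0.045 at r = 1, with power again 80.1%. Either reading of the unit leaves power at or above the stated figure.

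**Step 4: drop-outs.** The inflation to 284 counts drop-outs as contributing nothing. If all 284 per group contributed, power would be 89.1% even at r = 1. This simplification is also on the cautious side.

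**The case for a change.** The best case for a change is that success rests on this single test, so its power should be stated for that test, and that the correction would cost only a sentence or two. At r = 0.5, 160 subjects per group would do, so a reader who takes 213 completers as the threshold for adequate power could be misled. The unit also affects how the margin reads: with independent eyes, per-eye rates of 0.045 and 0.095 correspond to per-subject rates of 1 − 0.955² = 8.8% and 1 − 0.905² = 18.1%, a gap of 9.3 points.

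Some of this stands. The sample-size text does leave unsaid that it works as though r were 1 and counts completers only. The rest does not lead to a change:

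- The 213 is a planning minimum. The success rule in the SAP Executive Summary and SAP 5.3.1 turns on the upper confidence limit alone, and the model handles the pairing of eyes whatever the planning assumption was.
- Both documents list a table of historical adverse event rates (Protocol Table 12-1, SAP Table 7-1) that is not visible in the public text. It may give the denominators, so the plan cannot be faulted for omitting the unit of 0.045.
- How a per-eye margin translates to subjects is a question about the margin. The documents give no data on how often events are one-sided, and restating the power would not settle it.
- Substitute figures would be no firmer. The range above omits the site and site-by-treatment terms in SAP 5.3.1, which could lower power, so calling 80% a guaranteed worst case would overstate what is known. Nor does the plan tie the 284 randomized to a named set for the primary analysis: Protocol 12.6 refers to a safety analysis set that is not among the five in Protocol 12.2.

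**Conclusion.** No change follows. The 213 and the 80% are correct arithmetic for one independent outcome per subject. Applied to the planned per-eye comparison they are conservative: 213 subjects per group give between 80% and 97% power as the between-eye correlation runs from 1 to 0. When that correlation is unknown, counting each subject once is a fair choice, and the price is at most some surplus in sample size (213 against 160 per group at r = 0.5).

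This rests on the plan's rate of 0.045, a true difference of zero, the normal approximation, and a model without site terms. Whether the site terms reduce power is a separate matter that the choice between subjects and eyes does not affect. A sentence stating that each subject is counted as one unit would be harmless, but no decision in the trial depends on it.
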